6.3.3 Disease Parameters

6.3.3.1 Measurable Disease

Measurable lesions are defined as those that can be accurately measured in at least one dimension (longest diameter to be recorded) as:

- By chest x-ray: ≥ 20 mm;
- By CT scan:
 - Scan slice thickness 5 mm or under as ≥ 10 mm
 - \circ Scan slice thickness > 5 mm: double the slice thickness
- With calipers on clinical exam: ≥ 10 mm.

All tumor measurements must be recorded in millimeters (or decimal fractions of centimeters).

6.3.3.2 Malignant Lymph Nodes

To be considered pathologically enlarged and measurable, a lymph node must be ≥ 15 mm in short axis when assessed by CT scan (CT scan slice thickness recommended to be no greater than 5 mm). At baseline and in follow-up, only the short axis will be measured and followed.

6.3.3.3 Non-Measurable Disease

All other lesions (or sites of disease), including small lesions (longest diameter < 10 mm or pathological lymph nodes with \geq 10 to < 15 mm short axis), are considered non-measurable disease. Bone lesions, leptomeningeal disease, ascites, pleural/pericardial effusions, lymphangitis cutis/pulmonitis, inflammatory breast disease, and abdominal masses (not followed by CT or MRI), are considered as non-measurable.

Note: Cystic lesions that meet the criteria for radiographically defined simple cysts should not be considered as malignant lesions (neither measurable nor non-measurable) since they are, by definition, simple cysts.

'Cystic lesions' thought to represent cystic metastases can be considered as measurable lesions, if they meet the definition of measurability described above. However, if non-cystic lesions are present in the same patient, these are preferred for selection as target lesions.

6.3.3.4 Target Lesions

All measurable lesions up to a maximum of 2 lesions per organ and 5 lesions in total, representative of all involved organs, should be identified as **target lesions** and recorded and measured at baseline. Target lesions should be selected on the basis of their size (lesions with the longest diameter), be representative of all involved organs, but in addition should be those that lend themselves to reproducible repeated measurements. It may be the case that, on occasion, the largest

lesion does not lend itself to reproducible measurement in which circumstance the next largest lesion which can be measured reproducibly should be selected. A sum of the diameters (longest for non-nodal lesions, short axis for nodal lesions) for all target lesions will be calculated and reported as the baseline sum diameters. If lymph nodes are to be included in the sum, then only the short axis is added into the sum. The baseline sum diameters will be used as reference to further characterize any objective tumor regression in the measurable dimension of the disease.

Progressive disease by RECIST criteria (109) noted after the first re-staging scan may represent disease that was not detected on the pre-study scan, and a confirmatory scan will be required at the next scheduled re-staging evaluation unless clinically not indicated. If confirmed, progression should be dated by the initial time when the lesions are first detected. If progressive disease by RECIST criteria is seen after Cycle 3, but not confirmed on subsequent restaging scan, the scans from after Cycle 3 would serve as the baseline scan to evaluate for disease progression (110).

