3 STUDY IMPLEMENTATION

3.1 STUDY DESIGN

This trial is unique in that it is intended to establish the rationale and conditions for the use of oral DAC-THU and pembrolizumab therapy for NSCLC, EsC, and MPM. The goal is to establish the basis for subsequent evaluation of this treatment regimen in combination with other agents targeting MDSC, or adoptive immunotherapy regimens in patients with thoracic malignancies.

Patients potentially eligible for trial will be evaluated, and undergo subsequent eligibility assessment in the Thoracic Surgery Clinic/NCI. Patients meeting eligibility criteria will undergo baseline (if fresh tumor biopsy was not performed at screening) and post treatment tumor biopsies either by percutaneous image-guided FNA techniques in Interventional Radiology (Clinical Center/NIH) or endoscopic/thoracoscopic techniques in the CC operating room by Thoracic Surgery staff using standard of care practice guidelines. Tumor biopsies may be omitted at the discretion of the PI if risks outweigh potential research benefits.

The Phase I component will be a standard 3+3 design starting with oral DAC-THU on two consecutive days (preferably Tuesday and Wednesday) for two weeks out of three weeks for 9

weeks with incremental dose escalation as shown in Section **3.1.3**. Patients with high PD-L1 tumor expression will be combined with patients with low PD-L1 tumor expression to minimize accrual numbers required for the Phase I component of the study. Pembrolizumab will be administered on Wednesday, Thursday or Friday at a fixed intravenous dose of 200 mg q 3 weeks. One cycle is three weeks; one course is 9 weeks. Treatment evaluation including repeat tumor biopsy will be performed after one course of therapy (Week 10 +/- one week). Those patients exhibiting disease progression or unacceptable toxicities will be removed from study. Patients exhibiting stable disease or disease regression will be offered an additional course of therapy followed by treatment evaluation (without mandatory biopsy). Treatment will continue in this manner until off-study criteria have been met.

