3.3.1 General Guidance for Dose Modifications

- 3.3.1.1 Patients may continue to receive therapy provided the following criteria are met on Day 1 of each cycle:
 - Non-hematologic toxicity recovered to < Grade 2 (or tolerable Grade 2 or baseline).
 - No evidence of progressive disease.
- 3.3.1.2 In the event of an adverse event at least possibly related to the investigational agent, the dose of the investigational agent should be adjusted according to the parameters articulated above and guidelines listed in the Dose Delays / Dose Modifications tables shown below (**Table 9** and **Table 10**). If an adverse event is not covered in such tables, doses may be held at the discretion of the investigator for the subject's safety.

3.3.1.3 If patients fail to recover to CTCAE Grade 0-1, tolerable Grade 2 (or within 1 grade of starting values for pre-existing laboratory abnormalities), or baseline from a treatment-related adverse event attributable to DAC-THU within 42 days (2 cycles), they cannot receive additional DAC-THU. Patients may continue pembrolizumab monotherapy at the investigator discretion provided that discontinuation criteria for pembrolizumab toxicity have not been met.

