3.6.2 Off-Study Criteria

- Voluntary withdrawal for any reason, or noncompliance with protocol requirements
- Completion of the follow up period (see Section **3.4.4**)
- Progressive disease unless the patient is being followed for a serious adverse event related to the research. The event must resolve to baseline prior to removing from the study

- If the investigator determines that it is in the best interest of the patient to discontinue follow up
- Lost to follow up
- Death
- PI decision to close the study

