6.3.4.2 Metastatic Bone Lesions

Disease progression is considered if a minimum of two new lesions is observed on bone scan. New lesions seen by the end of Cycle 3 (with the first re-staging bone scan) may represent disease that was not detected on the pre-study scan, and a confirmatory scan will be required at the next scheduled re-staging bone scan unless clinically not indicated. If confirmed, progression should be dated by the initial time when the lesions are first detected. If new lesions are seen after Cycle 3, but no additional lesions are seen on confirmatory scans, the scans from post-Cycle 3 would serve as the baseline scan to evaluate for disease progression (109).

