6.3.5 Response Criteria for Radiographic Studies

6.3.5.1 Measuring of Soft Tissue Disease

a. Evaluation of Target Lesions

Complete Response (CR)

Disappearance of all target lesions. Any pathological lymph nodes (whether target or non-target) must have reduction in short axis to < 10 mm.

Partial Response (PR)

At least a 30% decrease in the sum of the diameters of target lesions, taking as reference the baseline sum diameters.

Progressive Disease (PD)

At least a 20% increase in the sum of the diameters of target lesions, taking as reference the smallest sum on study (this includes the baseline sum if that is the smallest on study). In addition to the relative increase of 20%, the sum must also demonstrate an absolute increase of at least 5 mm. (Note: the appearance of one or more new lesions is also considered progressions).

Note: For this study, determination of PD will not be made prior to the Day 60 evaluation.

Stable Disease (SD)

Neither sufficient shrinkage to qualify for PR nor sufficient increase to qualify for PD, taking as reference the smallest sum diameters while on study.

b. Evaluation of Non-Target Lesions

Complete Response (CR)

Disappearance of all non-target lesions and normalization of tumor marker level. All lymph nodes must be non-pathological in size (< 10 mm short axis).

Note: Tumor markers alone cannot be used to assess response. If tumor markers are initially above the upper normal limit, they must normalize for a patient to be considered in complete clinical response.

Non-CR/Non-PD (Stable Disease, SD)

Persistence of one or more non-target lesion(s) and/or maintenance of tumor marker level above the normal limits.

Progressive Disease (PD)

Appearance of one or more new lesions and/or *unequivocal progression* of existing nontarget lesions. *Unequivocal progression* should not normally trump target lesion status. It must be representative of overall disease status change, not a single lesion increase.

Although a clear progression of "non-target" lesions only is exceptional, the opinion of the treating physician should prevail in such circumstances, and the progression status should be confirmed at a later time by the review panel (or Principal Investigator).

c. Evaluation of Best Overall Response

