The best overall response is the best response recorded from the start of the treatment until disease progression/recurrence (taking as reference for progressive disease the smallest measurements recorded since the treatment started). The patient's best response assignment will depend on the achievement of both measurement and confirmation criteria.

Target Lesions	Non- Target Lesions	New Lesions	Overall Response	Best Overall Response when Confirmation is Required*
CR	CR	No	CR	\geq 4 wks. Confirmation**
CR	Non-CR Non-PD	No	PR	\geq 4 wks. Confirmation**
CR	Not evaluated	No	PR	
PR	Non- CR Non-PD Not evaluated	No	PR	
SD	Non- CR Non-PD Not evaluated	No	SD	Documented at least once \geq 4 wks. from baseline**
PD	Any	Yes or No	PD	
Any	PD***	Yes or No	PD	No prior SD, PR or CR
Any	Any	Yes	PD	

For Patients with Measurable Disease (i.e., Target Disease)

* See RECIST 1.1 manuscript for further details on what is evidence of a new lesion.

** Only for non-randomized trials with response as primary endpoint.

*** In exceptional circumstances, unequivocal progression in non-target lesions may be accepted as disease progression.

- d. Patients with a global deterioration of health status requiring discontinuation of treatment without objective evidence of disease progression at that time should be reported as "*symptomatic deterioration*." Every effort should be made to document the objective progression even after discontinuation of treatment.
- e. In some circumstances, it may be difficult to distinguish residual disease from normal tissue. When the evaluation of complete response depends on this determination, it is recommended that the residual lesions be investigated (fine needle aspirate/biopsy) before confirming the complete response status.

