10.1 METHODS OF ANALYSIS

Response rates will be calculated as the percent of patients whose best response is a CR or PR. Toxicity information recorded will include the type, severity, time of onset, time of resolution, and the probable association with the study regimen. Tables will be constructed to summarize the observed incidence by severity and type of toxicity.

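### No stated precedence between the confirm-and-re-baseline rule for first-restaging progression (6.3.3.4) and the RECIST criteria in 6.3.5.1, so the same patient can be a non-responder or a responder in the primary response rate

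*Combined protocol and SAP*

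**What the plan says.** **How the primary endpoint is built.** Section 10.1: "Response rates will be calculated as the percent of patients whose best response is a CR or PR". Section 6.3.5.1, part c, sets the window: "The best overall response is the best response recorded from the start of the treatment until disease progression/recurrence". The progression rule therefore decides whether a later partial or complete response counts.

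**Progression in the response criteria.** Section 6.3.5.1 requires an increase of at least 20% and at least 5 mm in the target sum, "taking as reference the smallest sum on study (this includes the baseline sum if that is the smallest on study". It also treats any new lesion as progression. Section 6.3.1 and part c of 6.3.5.1 use the same smallest-measurement reference. No progression may be called before the Day 60 evaluation, so the first formal call falls at the first restaging, after Cycle 3.

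**Progression in the lesion sections.** Section 6.3.3.4 says that RECIST progression at the first restaging may be disease missed before the study. It asks for confirmation at the following planned restaging unless this is clinically not indicated. A confirmed progression is dated back to its first detection. If it is not confirmed, "the scans from after Cycle 3 would serve as the baseline scan to evaluate for disease progression". Section 6.3.4.2 has parallel text for bone and a different count: "Disease progression is considered if a minimum of two new lesions is observed on bone scan".

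**Action at progression.** Section 3.1: "Those patients exhibiting disease progression or unacceptable toxicities will be removed from study". Section 3.3.1 makes "No evidence of progressive disease" a condition for treatment on Day 1 of each cycle. Section 3.6.1 lists progression as a reason to stop therapy. Section 3.6.2 takes the patient off study for "Progressive disease unless the patient is being followed for a serious adverse event related to the research". None of these mentions confirmation.

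**The concern.** Two sets of instructions cover the same scan, the first restaging at about week 10, and no section ranks them. Under one, progression there ends the count of best response. Under the other it is provisional until the next restaging and, if not confirmed, is set aside with a new reference for progression.

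At stake is the numerator of the phase II primary endpoint. The cohorts are small and each decision turns on a whole number of responders. If the rule is chosen after the scans have been seen, the choice can be affected by the result, and two analysts following the protocol in good faith can report different counts.

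**Working it through.** **1. One patient under both rules.** Take a patient with measurable disease who completes a full course, meets RECIST progression at the first restaging, does not meet it at the next, and later has a partial response against the original baseline, repeated at least 4 weeks later as 6.3.1 requires.

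| Step | 3.1, 3.3.1, 3.6 and 6.3.5.1 | 6.3.3.4 |
|---|---|---|
| First restaging | Progression; window closes; removal | Provisional; confirmation scan required |
| Next restaging | Not planned: 3.1 offers another course only for stable disease or regression, and 3.4.4 follows toxicity | Not confirmed; post-Cycle 3 scan becomes the progression reference |
| Later confirmed partial response | Outside the window | Can be inside the window |
| Scored in the response rate as | Non-responder | Can be a responder |

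If progression is confirmed, 6.3.3.4 dates it to first detection and the two rules agree. Only unconfirmed first-restaging progression separates them.

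**2. The designs as stated (section 10).** Let b(x; n, p) be the binomial probability of x responses in n. The design stops at r1 or fewer of n1 and is positive above r of n.

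- Early termination = sum of b(x; n1, p) for x = 0 to r1.
- P(positive) = sum over x = r1+1 to n1 of b(x; n1, p) × P[Bin(n − n1, p) ≥ r + 1 − x].

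| Cohort | r1/n1, r/n | p0, p1 | Early termination at p0: plan / recomputed | P(positive) at p0 | P(positive) at p1 |
|---|---|---|---|---|---|
| PD-L1 high | 4/10, 10/23 | 0.35, 0.60 | 75.2% / 0.7515 | 0.0977 | 0.8043 |
| PD-L1 low | 1/10, 5/29 | 0.10, 0.30 | 73.6% / 0.7361 | 0.0471 | 0.8051 |

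Both designs reproduce and meet their stated error rates, provided that a response has one definition.

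**3. How often a cohort sits one response short, at p0.**

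- High, stage 1: b(4; 10, 0.35) = 210 × 0.35^4 × 0.65^6 = 0.238.
- Low, stage 1: b(1; 10, 0.10) = 10 × 0.10 × 0.90^9 = 0.387.
- Passing stage 1 and ending at exactly 10 of 23: 0.052. Ending at exactly 5 of 29: 0.055.

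These are chances of being at the edge. A changed decision also needs a patient of the kind in step 1. The esophageal and mesothelioma cohorts have the same edge, 1 versus 2 of 10.

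**4. Illustration only.** The documents give no rate of such patients. Assume that a share q are non-responders under 6.3.5.1 and responders under 6.3.3.4, that the true rate under 6.3.5.1 equals p0, and that the whole cohort is scored by 6.3.3.4. P(positive) is then the step 2 formula at p0 + q:

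| q (assumed) | 0 | 0.01 | 0.03 | 0.05 | 0.10 |
|---|---|---|---|---|---|
| PD-L1 high | 0.098 | 0.115 | 0.156 | 0.204 | 0.352 |
| PD-L1 low | 0.047 | 0.069 | 0.126 | 0.201 | 0.431 |

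Both designs have little room below their stated alphas of 0.10 and 0.05. The table does not say what q is.

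**5. The bone rule.** A partial response in target lesions with one new bone lesion is progression under 6.3.5.1. Under 6.3.4.2 it is not progression on that ground. However, 6.3.4.2 speaks of bone scans, and neither section 2.2 nor Appendix 3 schedules one; CT, PET/CT and brain MR are listed. This limb is minor.

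**The case against.** The best defence is that the sections can be read together: 6.3.3.4 says when first-restaging progression is established, and 3.1, 3.3.1 and 3.6 say what follows once it is. Section 6.3.3.4 never says that treatment continues during confirmation, and it waives confirmation where not clinically indicated. Its stated reason, disease missed at baseline, also suggests new lesions rather than growth of measured ones.

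Part of this stands. A reader might infer that the plan orders treatment beyond progression; that is only an inference from the planned later restaging. But the reconciling reading is not written down. Section 6.3.5.1 makes no exception to its smallest-sum reference, 3.1 gives no path for a patient awaiting confirmation, and the trigger in 6.3.3.4 is RECIST progression, which includes target growth. The waiver adds discretion without settling precedence.

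Three other stronger readings fail:

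- A reader might infer that re-baselining makes a partial response easier to reach. It does not: 6.3.5.1 ties partial response to the original baseline, and the new reference in 6.3.3.4 is for progression only. The response rate changes because the best-response window stays open, so removing the re-baselining sentence alone would leave the confirmation rule in force.
- A reader might infer that the two-lesion bone rule is an equal source of error. With no bone scan scheduled, it is not.
- A reader might infer a planned duration-of-response result at risk. Section 6.3.1 defines duration, but section 1.1 does not list it as an objective and section 10 plans no analysis of it.

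The affected pattern also needs several steps in sequence and may be rare.

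**Conclusion.** The point holds as a gap in precedence. Section 6.3.3.4 on one side, and 6.3.5.1 with 3.1, 3.3.1, 3.6.1 and 3.6.2 on the other, give different answers for unconfirmed first-restaging progression, and the answer enters the primary response rate directly. One reclassified patient changes the decision when a cohort is one response short. At p0 that position has probability 23.8% (PD-L1 high) and 38.7% (PD-L1 low) at stage 1.

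The frequency of such patients is unknown. A reader might infer from the illustration that the false-positive rate is inflated by a known amount; the documents do not support that, because q is assumed throughout. The stated designs are sound under a single scoring rule. The point should be corrected before stage 1 is read; it does not invalidate the design.

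**What to change.** State in section 10.1, with a cross-reference in 6.3.3.4 and 6.3.4.2, that the primary response rate is scored by the RECIST 1.1 criteria in 6.3.5.1: smallest sum on study as the progression reference, any new lesion as progression, and best response closed at the first documented progression. State that the confirmation and re-baselining text in 6.3.3.4 and 6.3.4.2, and the two-lesion bone count, do not apply to that endpoint. List responses after an unconfirmed progression separately as a sensitivity result. Settle this before any cohort's stage 1 count is read.

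Separately, the sponsor must reconcile the passages on removal or continuation after a first progression (3.1, 3.3.1, 3.6.1 and 3.6.2 against 6.3.3.4 and 6.3.4.2). The scoring rule above does not choose between them.

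The cost is an amendment of wording, with no change to sample size or decision limits. The downside is that a few late responders may not count in the primary rate, although they would remain visible in the sensitivity listing.

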6.3.3.5 Non-Target Lesions

All other lesions (or sites of disease) including any measurable lesions over and above the 5 target lesions should be identified as **non-target lesions** and should also be recorded at baseline. Measurements of these lesions are not required, but the presence, absence, or in rare cases unequivocal progression of each should be noted throughout follow-up.

6.3.4 Methods for Evaluation of Measurable Disease

6.3.4.1 Guidelines for Evaluation of Measurable Disease

All measurements should be taken and recorded in metric notation using a ruler or calipers. All baseline evaluations should be performed as closely as possible to the beginning of treatment and never more than 4 weeks before the beginning of the treatment.

The same method of assessment and the same technique should be used to characterize each identified and reported lesion at baseline and during follow-up. Imaging-based evaluation is preferred to evaluation by clinical examination unless the lesion(s) being followed cannot be imaged but are assessable by clinical exam.

6.3.4.2 Metastatic Bone Lesions

Disease progression is considered if a minimum of two new lesions is observed on bone scan. New lesions seen by the end of Cycle 3 (with the first re-staging bone scan) may represent disease that was not detected on the pre-study scan, and a confirmatory scan will be required at the next scheduled re-staging bone scan unless clinically not indicated. If confirmed, progression should be dated by the initial time when the lesions are first detected. If new lesions are seen after Cycle 3, but no additional lesions are seen on confirmatory scans, the scans from post-Cycle 3 would serve as the baseline scan to evaluate for disease progression (109).

